#### 9.4.4 Selection of Doses in the Study

In the Phase 1 part of the Study E7438-G000-101, a Phase 1/2 study currently ongoing outside Japan, the recommended dose of tazemetostat has been determined to be 800 mg BID. The Phase 2 part of the study is ongoing at this dose level. Safety and tolerability of tazemetostat for subjects enrolled in Study E7438-G000-101 was assessed as of 15 Jan 2016. Tazemetostat was administered twice daily in 6 subjects for 100 mg, 3 subjects for 200 mg, 16 subjects for 400 mg, 46 subjects for 800 mg (including 1 subject from Study EZH-202), and 18 subjects for 1600 mg. One subject experienced Grade 4 thrombocytopenia at the dose level of 1600 mg BID; this event was also considered to be a DLT. The protocol-defined MTD was not reached. Treatment-related Grade 3 or 4 AEs observed at 800 mg BID were thrombocytopenia (2 subjects, 4.3%) and Grade 3 hepatocellular injury and Grade 3 hypertension (1 subject each, 2.2%) while no treatment-related Grade 3 or 4 AEs occurred at the dose level of 400 mg BID or lower doses. Based on the current clinical data, the starting dose of 800 mg, half of the maximum single dose of 1600 mg established outside Japan, was considered as suitable for this study whereas clinical data in Japanese subjects are not available.

#### 9.4.5 Selection and Timing of Dose for Each Subject

The selection and timing of the dose for each subject are provided in [Section 9.4.1 Treatment Administered](#).

#### 9.4.6 Blinding

The study will not be blinded.

#### 9.4.7 Prior and Concomitant Therapy

Any medication (including over-the-counter medications) or therapy administered to the subject during the study (starting at the date of informed consent until the final observation)

will be recorded on the CRF. For all drugs, the name, treatment start dates (or timing of starting treatment), treatment end dates, and reason for use will be recorded on the CRF. Concomitant drugs such as premedication, diagnostic agents, solutions, or fluid transfusions provided for surgery, medical examinations, or administrations will be excepted. For concomitant therapy, the name, treatment start dates (or timing of starting treatment), treatment end dates, and reason for use will be recorded on the CRF.

Treatment of complications or AEs, or therapy to ameliorate symptoms (including G-CSF, blood products, blood transfusions, fluid transfusions, antibiotics, steroids, antidiarrheal drugs, or tranquilizers) other than prohibited therapies and drugs may be given at the discretion of the investigator or subinvestigator but these therapies or drugs should be used in caution.

#### 9.4.7.1 Prohibited Concomitant Therapies and Drugs

The following drugs and therapies are prohibited:

- (1) From the time of subject enrollment to final study drug administration
  - Anti-tumor therapies (Subjects may receive corticosteroid for local or systemic symptom control prior to and while on study. Subjects may receive no more than 10 mg of prednisolone daily or equivalent corticosteroid when used for treatment of lymphoma related symptoms)
  - Any agent that potentially inhibits or induces CYP3A (see the Attachment separately provided to each site)
  - Other investigational agents
  
- (2) Cycles 0 and 1
  - To start or change the drugs for prophylactic use to prevent AE occurrence (continuous or treatment use is allowed).
  - Any agent that moderately inhibits or induces CYP3A or inhibits P-gp
  - H2 blockers, proton-pump inhibitors
  - Any antacids or other drugs known to raise gastric pH (C0D1 and C1D15 only). These drugs should be administered  $\geq 2$  hours before study drug administration and  $\geq 2$  hours after study drug administration if used in Cycle 1.

When anti-tumor therapies are implemented, study drug administration should be discontinued and protocol-specified off-treatment visits and procedures will be completed.

#### 9.4.7.2 Concomitant Drugs to be Used with Caution

Medications that are substrates of CYP3A, CYP2C8, CYP2C9, CYP2C19, and CYP2D6 and have a narrow therapeutic range (as shown in the Attachment separately provided to each site) should be avoided if possible.

#### 9.4.8 Prohibitions and Restrictions during Study Period

Grapefruit and grapefruit juice-containing products are not permitted for 1 week prior to dosing and throughout the study.

**Phototoxic Potential:** There are nonclinical data supporting a potential for phototoxicity, which has not been observed in clinical studies. Skin-related AEs include dry skin, pruritus, rash, and eczema. Based on the current limited clinical data, subjects should be instructed to take measures to avoid prolonged exposure to sunlight such as wearing sun screen and sun glasses, wearing protective clothing.

#### 9.4.9 Treatment Compliance

The investigator, subinvestigator, or clinical research coordinator will instruct subjects to follow appropriate use of study drug and record the treatment compliance. The CRA will review the treatment compliance during site visits and at the completion of the study.

Treatment compliance (date of administration, dose, time of administration [at second administration on the day before the PK sampling day, first administration on the PK sampling day, and second administration on C1D15] as shown in [Table 6](#)) and meal time before and after the first administration on C0D1 and C1D15 will be collected and recorded on the CRF.

#### 9.4.10 Drug Supplies and Accountability

The assigned pharmacist (or the designee) will be responsible for the accountability of all study drugs (dispensing, inventory, and record keeping) following the sponsor's instructions and adherence to GCP guidelines as well as local or regional requirements.

Under no circumstances will the investigator or subinvestigator allow the study drugs to be used other than as directed by this protocol. Study drugs will not be dispensed to any individual who is not enrolled in the study.

The assigned pharmacist (or the designee) must maintain an accurate and timely record of the following: receipt of all study drugs, dispensing of study drugs to the subject, unused study drugs that are returned by the subjects (unused study drug-1), unused study drugs that are shipped to site but not dispensed to subjects (unused study drug-2), and return of reconciled study drugs to the sponsor or (a sum of unused study drugs 1 and 2). This includes, but may not be limited to: (a) documentation of receipt of study drugs, (b) study drugs dispensing/return reconciliation log, (c) study drugs accountability log, (d) documentation of returns to the sponsor.

The study drugs and inventory records must be made available, upon request, for inspection by a CRA or a representative of a health authority. Upon completion of unused drug accountability procedures and documentation of study drugs dispensing/return reconciliation log and documentation of returns to the sponsor by the assigned pharmacist (or designee), all unused study drugs and empty bottles are to be returned to the sponsor. Unused study drugs

that are returned from the site are hand-delivered to CRAs and to be returned to the sponsor's designated depot.

Drug accountability will be reviewed by the CRA during site visits and at the completion of the study, and throughout the study.

## 9.5 Study Assessments

### 9.5.1 Assessments

#### 9.5.1.1 Demography

Subject demography information will be collected at Screening. Demography information includes Subject ID Number, date of written informed consent, date of birth (or age), sex, race, and ethnicity.

#### 9.5.1.2 Pre-treatment Assessments

##### 9.5.1.2.1 MEDICAL HISTORY AND CURRENT MEDICAL CONDITIONS

Medical and surgical history and current medical conditions will be recorded at Screening. All medical history that is considered to have effects on safety, efficacy, or PK by the investigator or subinvestigator, and medical conditions that are identified at Screening must be noted on the CRF.

The following information on primary disease and its prior therapies will be collected at Screening and noted on the CRF.

#### (1) Primary disease

- Date of diagnosis
- Diagnosis
- Clinical staging at Screening (Ann Arbor staging) ([Carbone, et al., 1971](#))
- B symptoms (unexplained fever more than 38 °C, drenching night sweats, unexplained weight loss of more than 10% of usual body weight over 6 months)

- CCI

#### (2) Prior therapies for primary disease

- 1) Chemotherapy (type of therapy, best overall response, name of therapy/drug, start dates, end dates)
- 2) Radiotherapy (site of radiation, deterioration after radiotherapy, first date of radiation, last date of radiation)
- 3) Autologous stem cell transplantation (with or without autologous stem cell transplantation, date of transplantation)

### 9.5.1.3 Efficacy Assessments

Tumor assessment will be performed by investigator or subinvestigator using “The Lugano Classification (CT-Based Response)” (Cheson, et al., 2014). Overall response and best overall response (BOR) (best response recorded at the designated visits during the study) will be assessed. Perform CT scans at Screening, every 8 weeks (starting at Cycle 1/Day 1) during Cycles 2-6, every 12 weeks starting at Cycle 7 (Cycle 7/Day 1) and beyond, and discontinuation.

A bone marrow aspiration or biopsy will be performed at screening for evaluation of bone marrow infiltration of tumor. After the study drug administration, perform bone marrow aspiration or biopsy if the result of screening was positive or unconfirmed and when to confirm CR as best of response or if clinically indicated.

Preliminary anti-tumor activity will be objective response rate (ORR) as defined by “The Lugano Classification (CT-Based Response)” (Cheson, et al., 2014). ORR is defined as the proportion of subjects who have a BOR of CR or PR.

Details of procedure of efficacy assessments will be provided in the Attachment “Overall response evaluation criteria” separately provided to each site.

### 9.5.1.4 Pharmacokinetic, Pharmacodynamic, Pharmacogenomic, and Other Biomarker Assessments

The sampling schedule of PK, pharmacogenomics, and other biomarker assessments of tazemetostat is shown in Table 6 and below.

#### 9.5.1.4.1 PHARMACOKINETIC ASSESSMENTS

Plasma and urine concentrations of tazemetostat and plasma concentrations of its metabolite, ER-897387 will be measured to evaluate pharmacokinetics in all of the registered subjects. Blood samples and urine samples will be collected at the time points designated in Table 6. Detailed blood and urine sampling schedules for PK assessment are shown in Table 3 and Table 4, respectively. Procedures for collection, handling, and shipping for PK samples will be provided in a separate manual.

Plasma concentrations of tazemetostat and ER-897387 and urine tazemetostat concentrations will be measured by validated methods using liquid chromatography with tandem mass spectrometry (LC-MS/MS).

For PK assessment, actual time and date of PK blood samplings, starting time of urine collection (defined as the time of first administration of study drug), ending time of urine collection, urine volume, and tween80 volume will be recorded in the CRF.

**Table 3 Blood Sampling Schedule for Pharmacokinetic Assessment  
Tazemetostat and ER-897387**

Day	Sampling Time	Allowance (as a Target)
C0D1	Predose	Within 180 minutes before dosing
	0.5 hours postdose	±10 minutes
	1 hour postdose	±10 minutes
	2 hours postdose	±10 minutes
	4 hours postdose	±10 minutes
	6 hours postdose	±10 minutes
	8 hours postdose	±10 minutes
	10 hours postdose	±10 minutes
	12 hours postdose	±10 minutes
C0D2	24 hours postdose	±60 minutes
C0D3	48 hours postdose	±60 minutes
C0D4	72 hours postdose	±60 minutes
C1D3	Predose of first administration	Within 120 minutes before dosing
C1D8	Predose of first administration	Within 120 minutes before dosing
C1D15 (Blood sampling after first administration of study drug should be performed before second administration)	Predose of first administration	Within 60 minutes before dosing
	0.5 hours postdose of first administration	±10 minutes
	1 hour postdose of first administration	±10 minutes
	2 hours postdose of first administration	±10 minutes
	4 hours postdose of first administration	±10 minutes
	6 hours postdose of first administration	±10 minutes
	8 hours postdose of first administration	±10 minutes
	10 hours postdose of first administration	±10 minutes
	12 hours postdose of first administration	±10 minutes
C1D22	Predose of first administration	Within 120 minutes before dosing
C2D1	Predose of first administration	Within 120 minutes before dosing

C#D# = Cycle #/Day #.

**Table 4 Urine Sampling Schedule for Pharmacokinetic Assessment  
Tazemetostat**

Day	Sampling Time	Allowance (as a Target)
C0D1	Predose (urine sampling)	From the time of wake-up to just before dosing
C0D2	0–24 hours postdose (urine collection)	–
C0D3	24–48 hours postdose (urine collection)	–
C0D4	48–72 hours postdose (urine collection)	–
C1D15	0–12 hours postdose of first administration (urine collection) (should be ended before second administration)	–

C#D# = Cycle #/Day #.

#### 9.5.1.4.2 PHARMACODYNAMIC, PHARMACOGENOMIC, AND OTHER BIOMARKER ASSESSMENTS

CCI

CCI

CCI

### 9.5.1.5 Safety Assessments

Safety assessments are shown in [Table 6](#) (Schedule of Procedures/Assessments) and below.

Safety assessments include monitoring and recording all AEs, including all grading of Common Terminology Criteria for Adverse Events (CTCAE) v4.03, and SAEs; regular laboratory evaluation for hematology, blood chemistry, and urine values; and periodic measurement of vital signs, ECGs, echocardiograms/MUGA scans to assess LVEF, ECOG-PS, and physical examinations.

#### 9.5.1.5.1 ADVERSE EVENTS AND EVENTS ASSOCIATED WITH SPECIAL SITUATIONS

An AE is any untoward medical occurrence in a subject. An AE does not necessarily have a causal relationship with the medicinal product. For this study, the study drug is tazemetostat.

The criteria for identifying AEs in this study are:

- Any unfavorable and unintended sign (including an abnormal laboratory finding), symptom, or disease found after the time of informed consent, whether or not considered

related to the investigational product (Note: Every sign or symptom should not be listed as a separate AE if the applicable disease [diagnosis] is being reported as an AE)

- Any new disease or exacerbation of an existing disease. However, worsening of the primary disease should be captured under efficacy assessments as disease progression rather than as an AE.
- Any deterioration in nonprotocol-required measurements of a laboratory value or other clinical test (eg, ECG or x-ray) that results in symptoms, a change in treatment, or discontinuation of study drug
- Recurrence of an intermittent medical condition (eg, headache) not present pretreatment (Baseline)
- An abnormal laboratory test result should be considered an AE if the identified laboratory abnormality leads to any type of intervention, withdrawal of study drug, or withholding of study drug, whether prescribed in the protocol or not

All AEs observed during the study will be reported on the CRF. All AEs, regardless of relationship to study drug or procedure, should be collected beginning from the time the subject signs the study ICF through the final observation visit. SAEs will be collected until the final observation visit. Subjects who fail screening primarily due to AE(s) must have the AE(s) leading to screen failure and its seriousness reported on the CRF.

Any laboratory abnormality considered to constitute an AE should be reported on the CRF. Abnormal laboratory values should not be listed as separate AEs if they are considered to be part of the clinical syndrome that is being reported as an AE. It is the responsibility of the investigator or subinvestigator to review all laboratory findings in all subjects and determine if they constitute an AE. Medical and scientific judgment should be exercised in deciding whether an isolated laboratory abnormality should be classified as an AE.

Abnormal ECG (QTc) results, if not otherwise considered part of a clinical symptom that is being reported as an AE, should be considered an AE if the QTc interval is more than 450 ms and there is an increase of more than 60 ms from baseline. Any ECG abnormality that the investigator or subinvestigator considers as an AE should be reported as such.

All AEs must be followed until last visit for final observation or until resolution, whichever comes first. However, if other anticancer treatments should be implemented as soon as possible considering the deterioration of subject's physical condition, the last visit will be allowed within 30 days after the last dose (ie, before the start of other anticancer treatments). All SAEs must be followed to resolution or, if resolution is unlikely, to stabilization.

Every effort must be made by the investigator or subinvestigator to categorize each AE according to its severity and its relationship to the study treatment.

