**Table 2 Tazemetostat Dose Reduction and Interruption Instructions**

Tazemetostat -related Toxicity		During Therapy d	Dose adjustment d
Grade 1 and Tolerable Grade 2 a		Continue tazemetostat	Maintain dose level
Intolerable Grade 2 a and Grade 3 b		Interrupt tazemetostat until resolved to Grade $\leq$ 1 or baseline c	Dose reduction by one dose level
Grade 3 and Grade 4 neutropenia	ANC $\geq 0.75 \times 10^9/L$	Continue tazemetostat	Maintain dose level
	ANC $< 0.75 \times 10^9/L$	Interrupt tazemetostat until resolved to ANC $\geq 0.75 \times 10^9/L$ e	Dose reduction by one dose level
Grade 4 c		Interrupt tazemetostat until resolved to Grade $\leq$ 1 or baseline c	Discuss with sponsor or discontinue tazemetostat

ANC = absolute neutrophil count.

a: Tolerability of Grade 2 toxicities will be judged by the study investigators.

b: Dose interruption and reduction is not necessary for Grade 3 thrombocytopenia, anemia and Grade 3 or 4 leukopenia, lymphopenia and laboratory abnormalities that are not clinically relevant. Initiate optimal medical management for nausea, vomiting, and/or diarrhea prior to any study treatment interruption or dose reduction.

c: Laboratory abnormalities judged to be non-life threatening, will be managed as Grade 3.

d: Discuss with the sponsor when to consider the dose interruption and adjustment other than instructions.

e: To minimize the duration of interruption, assessment at least every 7 days is recommended. A delay of tazemetostat for more than 28 days due to any toxicity must be discussed with the sponsor before treatment can be resumed.

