5.6.4 Laboratory Values

Laboratory results will be summarized using Système International (SI) units, as appropriate. For all quantitative parameters listed in [Section 9.5.1.5.3 Safety Assessments \(Laboratory Measurements\)](#), the actual value and the change from baseline to each postbaseline visit and to the last observation will be summarized by visit using descriptive statistics. Qualitative parameters listed in [Section 9.5.1.5.3](#) will be summarized using frequencies (number and percentage of subjects), and changes from baseline to each postbaseline visit and the last observation will be reported using shift tables. Percentages will be based on the number of subjects with both nonmissing baseline and relevant postbaseline results.

CTCAE v4.03 will be used to identify subjects with treatment-emergent markedly abnormal laboratory values (TEMAVs). Except for phosphate, a TEMAV is defined as a post baseline

value with an increase from baseline to a grade of 2 or higher. For phosphate, a TEMAV is defined as a postbaseline value with an increase from baseline to a grade of 3 or higher. When displaying the incidence of TEMAVs, each subject will be counted once in the laboratory parameter high and in the laboratory parameter low categories, as applicable. TEMAVs will be summarized by study overall.

The following combination of abnormal laboratory tests will be presented in listing.

- Elevated AST or ALT lab value that is greater than or equal to 3X the upper limit of normal
AND
- Elevated total bilirubin lab value that is greater than or equal to 2X the upper limit of normal
AND AT THE SAME TIME
- Alkaline phosphatase lab value that is less than 2X the upper limit of normal

The measured values for quantitative data will be displayed over time using Box plot.

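### The SAP's only CTCAE-based laboratory table (TEMAV) cannot separate Grade 3-4 from Grade 2, and some severe values need not be recorded as AEs, so their grade may be tabulated nowhere

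*Protocol*

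**What the plan says.** **AE capture (Protocol 9.5.1.5.1).** Three statements bear on laboratory values.
- The first AE criterion is broad: "Any unfavorable and unintended sign (including an abnormal laboratory finding), symptom, or disease found after the time of informed consent".
- The last criterion is tied to action: "An abnormal laboratory test result should be considered an AE if the identified laboratory abnormality leads to any type of intervention", or to study drug being stopped or held back.
- The section then adds a discretion: "Medical and scientific judgment should be exercised in deciding whether an isolated laboratory abnormality should be classified as an AE". No grade is named above which a laboratory value must be recorded.

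**Action required (Protocol Table 2, drug-related toxicity from Cycle 2).** Footnote b says "Dose interruption and reduction is not necessary for Grade 3 thrombocytopenia, anemia and Grade 3 or 4 leukopenia, lymphopenia". In the rows headed "Grade 3 and Grade 4 neutropenia", treatment continues unchanged at ANC 0.75 x10^9/L or above; below that it is interrupted and reduced. In Cycles 0 and 1, Protocol 9.4.1.1.1 leaves interruption to clinical judgment when there is no DLT.

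**Laboratory analysis (SAP 5.6.4).** Outside phosphate, a TEMAV is a post-baseline "value with an increase from baseline to a grade of 2 or higher"; for phosphate the threshold is Grade 3. Each subject counts once for high and once for low, and "TEMAVs will be summarized by study overall". Quantitative parameters otherwise get descriptive statistics by visit and box plots. Shift tables are planned for qualitative parameters only.

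**Graded severity (SAP 5.6.3).** The highest CTCAE grade is tabulated for TEAEs and for treatment-related TEAEs.

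**The concern.** Two features combine. The by-grade AE tables contain only what the investigator chose to record, and for isolated laboratory abnormalities that choice has no grade rule. The laboratory table does not depend on AE recording, but it uses a single cut at Grade 2 and so cannot show how severe the abnormality was.

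For a no-action Grade 3 or 4 cytopenia that is not recorded as an AE, the plan has no table that shows its grade. Safety is the first secondary objective, and Protocol 7.3.3 reports cytopenias as the related SAEs and Grade 4 thrombocytopenia as the only DLT overseas. A Grade 3-4 laboratory count that does not rest on AE reporting in an open-label study would be useful, and the SAP text does not specify one.

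**Working it through.** The plan states no figure on this point, and its sample size is expressly not statistical, so there is nothing to reproduce. The check has two parts.

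**1. Which severe values carry no mandated action?** Inputs are the CTCAE bands in SAP 13.1, Protocol Tables 1 and 2, and Protocol 9.4.1.1.1.

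Neutrophils: Grade 3 is 0.5 to <1.0 x10^9/L and Grade 4 is <0.5. Set against the 0.75 cut in Table 2:

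| ANC (x10^9/L) | CTCAE grade | Table 2 (Cycle 2 on, drug-related) |
|---|---|---|
| 0.75 to <1.0 | 3 | continue, same dose |
| 0.5 to <0.75 | 3 | interrupt, reduce |
| <0.5 | 4 | interrupt, reduce |

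An interruption brings the value under the action-based AE criterion. From Cycle 2, then, only the first row escapes a mandatory AE.

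Other cytopenias from Cycle 2, under footnote b: Grade 3 thrombocytopenia, Grade 3 anemia, and Grade 3 or 4 leukopenia and lymphopenia.

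Cycles 0 and 1: in Table 1, Grade 4 neutropenia is a DLT if it lasts more than 7 days or if growth factor is needed. An afebrile Grade 4 episode of 7 days or less without growth factor is not a DLT on that line, and interruption is then a matter of judgment. Leukopenia and lymphopenia are not named among the hematological DLTs.

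**2. What does the TEMAV table show?** Rule (non-phosphate): TEMAV = 1 if post-baseline grade > baseline grade and post-baseline grade >= 2; otherwise 0. Assumed example: six subjects, all Grade 0 at baseline, one parameter, one direction.

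| Worst post-baseline grades | TEMAV | Grade 3 or higher |
|---|---|---|
| 2, 2, 2, 2, 2, 2 | 6/6 (100%) | 0/6 (0%) |
| 4, 4, 4, 4, 4, 4 | 6/6 (100%) | 6/6 (100%) |
| 2, 2, 3, 3, 4, 4 | 6/6 (100%) | 4/6 (66.7%) |

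The TEMAV count is the same in all three cases, while the Grade 3 or higher count runs from 0 to 6. With six subjects, each one moves a rate by 1/6 = 16.7 points. A subject going from Grade 2 to Grade 4 also counts as one TEMAV, the same as one going from Grade 0 to Grade 2.

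**The case against.** **The AE definition already covers these values.** A reader might infer that a laboratory abnormality is an AE only if it led to action. The text does not say that: the first criterion needs no intervention, and the investigator must review all laboratory findings. This objection stands against any claim that such values are excluded. It does not remove the discretion, because the same section asks the investigator to decide whether a finding is an AE. QTc, by contrast, has a numeric AE trigger in that section.

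**Most severe cytopenias are caught elsewhere.** This largely stands. A reader might infer that any Grade 4 cytopenia can slip through. Drug-related Grade 4 thrombocytopenia is a DLT in Cycles 0 and 1, and from Cycle 2 the Grade 4 row calls for interruption. It could pass only if footnote c ("Laboratory abnormalities judged to be non-life threatening, will be managed as Grade 3") and then footnote b were both applied. Transfusion or growth factor use is an intervention and so makes the value an AE. Table 2 is limited to drug-related toxicity from Cycle 2. That narrows where action is waived, but also where it is required.

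**The overseas comparison is intact.** A reader might infer that comparison with the Grade 3-4 rates in the dose rationale is lost. It is not. Those are rates of treatment-related AEs (Protocol 7.4 and 9.4.4), and SAP 5.6.3 plans the matching table.

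**Extremes are visible anyway.** Minimum, maximum and box plots are planned, and with about six subjects they are legible. They carry no grade, however, and a minimum by visit does not say how many subjects reached Grade 3 or 4.

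**The table shells may add a grade table.** They are a separate document (SAP 11), so this cannot be excluded. But Protocol 9.7.1.8.4 assigns the TEMAV definition to the SAP, which gives one threshold. For QTcF, SAP 5.6.6 reports three absolute cuts.

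**Conclusion.** The point holds as a reporting gap in a secondary safety summary. The SAP text plans no laboratory table that separates Grade 3-4 from Grade 2 outside phosphate, and a defined group of severe values may go unrecorded as AEs. Those values would be counted as TEMAVs if treatment-emergent, with the grade hidden, and would be visible only in ungraded ranges and plots.

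It would go too far to conclude that severe laboratory toxicity disappears from the report. A value recorded as an AE appears by grade, and a DLT is reported as such.

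The size is illustrative: the same TEMAV result of 6/6 is compatible with 0/6 to 6/6 at Grade 3 or higher. That rests on an assumed set of six subjects at Grade 0 at baseline. The documents give no expected frequency of unrecorded severe values, so the actual loss may be small or nil. The DLT endpoint and the tolerability rule are unaffected.

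**What to change.** In SAP 5.6.4, keep the TEMAV table and add a shift table of baseline CTCAE grade by worst post-baseline grade, for each graded parameter and direction. From it, give the number (%) of subjects with treatment-emergent Grade 3 and with treatment-emergent Grade 4, irrespective of whether the value was recorded as an AE. Name the table in the SAP text, so that it does not depend on the shells.

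The cost is one extra table. The laboratory values are already collected, and CTCAE grading is already needed to derive TEMAVs. No new data, visits or change to the primary analysis are required.
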